Additionally, there are certain risks and discomforts that may be associated with exercise that include temporary shortness of breath, muscle fatigue, sweating, and physical discomfort. Muscles may be sore up to three days after performing the exercise. Also, there exists the possibility of an undiagnosed medical problem that may surface during the exercise. During testing, participants will be carefully observed by members of the research team to reduce these risks associated with exercise.

Adverse Events: Adverse events will be defined as any untoward medical occurrence in study participants or others immediately involved in the performance of the protocol, which does not necessarily have a causal relationship with the study treatment, but results in a change in intervention, daily function, hospitalization or rated category 3 or above using the National Cancer Institute Common Terminology Criteria for Adverse Events (CTCAE) v3.0.²⁰⁹ Expected events such as slight muscle soreness consistent with exercise, or those consistent with a participant's prior medical history not sufficient to alter the intervention will not be considered an AE. Staff involved in performance of the protocol (e.g. trainers, dieticians, coordinators) will continually monitor participants for adverse events throughout the intervention, and study staff will assess adverse events at every testing visit as well as during regularly scheduled telephone assessments with all randomized participants.

If study staff, tester, participant, caregiver or exercise instructor reports adverse events or complaints, relevant information will be collected and documented.

The participant will be evaluated by the unblinded investigator identified in the protocol. The investigator will have access to training logs, telephone assessment forms, and all study-related testing results. The

APEX Protocol 22 April 2016

investigator will determine the severity (according to the CTCAE) and relatedness of the AE to the intervention. The investigator will identify adverse events of clinical concern, those that may require further workup, or suggest that additional participation in the intervention might be a safety risk. These AEs will first be discussed with the participant and then communicated to the study staff or providers with participant's consent and as appropriate.

All maximal exercise testing will be monitored by an appropriate medical monitor. If the subject has performed a maximal exercise test in the past, we will, with the participant's consent, request the records from the testing to use as baseline ECG. Incidental research findings noted by the medical monitor (e.g. ECG abnormalities) will be discussed with the participant. Participants will be referred to a provider as requested. Imaging (e.g. MR, DXA) will be formally read only when required by the protocol and as outlined to the participant in the consent form. All adverse events will be reported to the investigator, study coordinator, the Data Safety Monitoring Board and the Human Subjects Committee per KUMC Human Subject Committee reporting policies.

Adequacy of Protection Against Risk

Recruitment and Informed Consent: Recruitment occurs by referrals from organizations serving large numbers of older adults, public service announcements through media, physician referral, and word of mouth.

We are very sensitive to issues related to the subject's ability to understand the elements of consent and their capacity to make decisions. Individuals with dementia will be excluded from the study. Informed consent will be obtained by study staff (as the designee for [name]); the purposes of the study, its assessment procedures, and risks and benefits are explained. The original signed consent form is kept with the subject's confidential file and a copy is given to the subject.

Protection Against Risk: All research data are maintained confidentially by numerical code in password-protected databases. All paper copies are filed by number in accordance with professional standards of privileged information. Confidentiality is strictly safeguarded by HIPAA-compliant standards.

Empathetic and professional staff mitigates risk of embarrassment. An experienced nurse clinician performs venipuncture. All women in the study will be post-menopausal and thus not at risk of pregnancy, mitigating the risks of low dose radiation from DEXA scanning. The risk from radiation exposure of this magnitude is too small to be measured directly and is considered to be negligible when compared with other everyday risk. Risk from MRI is mitigated by trained technicians who thoroughly screen participants for exclusionary conditions prior to each MRI session.

To protect against and minimize potential risks during the assessment of VO₂ peak, subjects will be carefully evaluated during the clinical assessment with a physical examination and a resting ECG. The subjects will be screened to exclude those with a history of ischemic heart disease. During the exercise test, a physician will be present and monitor the subject's heart rhythm by electrocardiography and blood pressure. American College of Sports Medicine (ACSM) guidelines will be used to determine whether the exercise test should be terminated early. Criteria for immediate termination include chest discomfort, ST-segment depression (>2mm), nervous system symptoms (i.e., ataxia, dizziness), and sustained ventricular tachycardia.

Risks for the treadmill exercise intervention are similar to those of exercise testing as detailed above. Participants will be initially supervised by a fitness specialist to ensure safety. Kill switches and handrails are standard on the treadmills. The program will begin with light exercise and progressively increase in intensity. Sessions are supervised by a trained professional who will focus on avoiding injuries and adapting the program to participants' needs. If subjects develop chest discomfort, other symptoms (for example, dizziness), or injury, the session will be discontinued immediately.

Florbetapir PET Results Disclosure: The KU ADC is disclosing results of the Florbetapir PET scans to participants. This is done under a separate consent to the exercise trial outlined in this proposal although we are including information here regarding the rationale for disclosure and how risks will be mitigated.

With the advent of molecular imaging, there is an increasing interest in the use of AD biomarkers in diagnosis and risk assessment. As of February 2011, these techniques are confined to the research arena although with the expected approval of agents by the FDA in the near future, their use will likely soon become widespread in clinical use. The KU ADC is at the forefront in this biomarker research and the KU ADC's Florbetapir substudy creates important opportunities that allow us to participate in and shape the national conversation on how AD biomarkers are used for risk assessment. Additionally, identifying a cohort of individuals with and without asymptomatic cerebral amyloidosis is designed to provide the essential foundation for performing necessary rigorous studies assessing AD prevention strategies.

In our review of the literature, we believe our choice to reveal amyloid status has several advantages and relatively low risks to the participants. Hallmark studies in this area (Roberts et al., 2005; Carpenter et al., 2008) indicate that most people want to know if they have a specific diagnosis (risk for AD or the diagnosis; Bamford et al. 2004; Carpenter & Dave, 2004). In these studies, reports of anxiety and depression were actually higher before diagnosis than after, and low reporting of depressive symptoms persisted throughout the 6-week, 6-month and 1-year follow up periods. Thus, the overwhelming majority of people who received news of their elevated risk profile or a diagnosis of AD did not experience grief, depression, or anxiety as a result of that disclosure. Thus "bad news" does not necessarily lead to a catastrophic emotional reaction (Aminzadeh et al., 2007; Carpenter et al., 2008)

Although we do not anticipate many participants to experience reactive depression or anxiety in response to amyloid status disclosure, we are putting in place safety monitoring procedures to detect those individuals who do experience distress and provide mental health referrals when appropriate. Based on the literature (Roberts et al., 2005; Carpenter, 2009; Green et al., 2009), we anticipate 5 categories of possible reaction that need to be monitored: relief, depressive reaction, anger, anxiety, or a blend of these four categories. Negative reactions were more likely to occur when the participant is male, lower educated, and young (below age 60). Knowing these are demographic characteristics will help the clinical research team to expedite the identification of individuals experiencing distress. In the current study we include the identical measures used in the hallmark studies to insure that we are using best-practices to monitor for adverse reaction to disclosure of asymptomatic cerebral amyloidosis.

Non-elevated Amyloid Group: We will recruit individuals with non-elevated amyloid PET scans who have a mean SUVR (in 6 regions of interest) of 1.0 and greater to be enrolled into the trial as part of the non-elevated amyloid group. Based on our first 84 non-elevated participants screened for the study, this represents about 1/3rd of those with non-elevated amyloid PET scans. Participants will be recruited by letter or phone calls to those who have been previously screened and meet the criteria or during in-person screening visits until a total of 50 nonelevated participants are enrolled.

SUVR (Standard Uptake Value Ratio) represents a ratio of the retention of radiotracer in the brain compared to the patient's control region of the cerebellum. A higher is believed to reflect higher levels of amyloid in the brain although in this group of individuals who do not evidence of amyloid deposition given their non-elevated status, the relevance of the SUVR value remains uncertain. Nevertheless, this group is of scientific interest given some early data suggesting the group may be enriched with individuals who accumulate amyloid over time.

Rationale for not disclosing SUVR values: Participants will be informed that they are in a group representing 1/3rd of those with non-elevated scans that have been selected as eligible to participate based on computer algorithm. Our current practice is not to communicate information on patient's SUVR values and we believe this continues to be important until more data is available to suggest that SUVR values are shown to be clinically relevant. There is currently no consensus or evidence that within non-elevated participants SUVR values have clinical relevance. It remains unclear that an SUVR value, especially in the non-elevated range, provides any predictive information on risk. Additionally, it remains unclear whether the sensitivity and precision of the measure influences how these values can be interpreted. Not disclosing SUVR values to participants is the current practice for the national Alzheimer's Disease Neuroimaging Initiative. We have a scientific interest in the group of individuals in the top third of SUVR measures as there is early evidence that those with higher amyloid burdens may accumulate amyloid at a more rapid rate than others. Whether individuals who accumulate amyloid are at higher risk of cognitive change is not yet known although given that our primary aim is to assess the impact of aerobic exercise on amyloid accumulation.

Given the burden and expense of amyloid scanning, MRI scanning, and a one-year exercise program, it is not feasible to enroll a sample of all non-elevated participants.

Potential Benefits of the Proposed Research to the Subjects and Others

Subjects potentially benefit from participation in a supervised exercise program.

Importance of the Knowledge to be Gained

Society benefits from research advances in aging and the maintenance of cognitive and brain health. Improved fitness through supervised rehabilitation programs may represent an important therapeutic or preventive strategy for dementia. This study will enhance our understanding of the role of exercise in promoting healthy brain aging. Potential benefits outweigh the minimal risks of this research.

Data Safety and Monitoring Plan

An internal safety committee will meet quarterly to review adverse events and the overall safety of the ongoing trial. The committee will be composed of three clinicians: [name], [name], and [name]. The primary responsibilities of the DSMB are to 1) periodically review and evaluate the accumulated study data for participant safety, study conduct and progress, and efficacy when planned in the protocol, and 2) make recommendations to the PI concerning the continuation, modification, or termination of the trial.

Should a study participant experience an AE, relevant information will be collected and documented, and the AE will be reviewed by the appropriate investigator within 24 hours. If the investigator determines the AE is directly related to the study, raises concern about increased risk to the participant or overall safety of the study design, the safety committee will be notified within 24 hours. The DSMB will evaluate the AE and will make recommendations based on the protocol (e.g. stopping rules).

Women and Minority Inclusion in Clinical Research

Inclusion of women: Women are included in all studies described. We expect that approximately 50% of the subjects will be women.

Inclusion of minorities: All minority groups are encouraged to participate in this and all our research projects. We place an extra emphasis on the recruitment of minorities through the KU ADC and the Landon Center on Aging. The ADC Education Core recently hired a minority outreach coordinator to increase enrollment of African Americans into ADC studies. The Landon Center on Aging community outreach effort specifically targets the Hispanic and African American populations through activity in service agencies for these populations and with targeted advertising in minority publications. In 2003, the University of Kansas Medical Center's outpatient population was composed of 18% African-American, 10% Hispanic, 1% Asian, and 3% other. We expect this proportion of minorities will be reflected in our enrollment. All minority groups are encouraged to participate in the research projects.

REFERENCES

1. Middleton LE, Yaffe K. Targets for the prevention of dementia. *J Alzheimers Dis*;20:915-924.

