This study examines the effects of aerobic exercise on AD pathophysiology (amyloid burden) and associated "downstream" neurodegeneration (regional atrophy) and cognitive decline in preclinical AD. The proposal extends our ongoing work on the role of exercise to promote a healthier brain and capitalizes on our new status as an AD Center (KU ADC; P30AG035982). We will examine the effects of a 52-week aerobic exercise program in 120 individuals, 70 with preclinical AD and 50 with nonelevated amyloid. We will use existing clinical research infrastructure of the KU ADC to recruit 400 sedentary, cognitively normal (CDR 0) individuals age 65 and older for screening with Florbetapir PET imaging to enroll 70 preclinical AD participants (defined as cognitively normal participants with elevated cerebral amyloid) and 50 individuals with non-elevated cerebral amyloid. Participants will be randomized in a 2:1 ratio to either aerobic exercise or control. Exercise training will occur in a community setting through the network of KUMC approved facilities.

Aim 1: Determine the effect of aerobic exercise on amyloid burden in individuals with preclinical AD (cognitively normal with elevated cerebral amyloid) and those without elevated amyloid. We hypothesize that 52 weeks of aerobic exercise will be associated with lower amyloid burden as measured by Florbetapir PET imaging. Our primary amyloid burden measure will be mean change from baseline to 52 weeks in Florbetapir cortical-to-cerebellar ratio averaged across 6 regions of interest (frontal, temporal, parietal, anterior cingulate, posterior cingulate, and precuneus).

Aim 2: Determine if aerobic exercise attenuates structural brain changes in preclinical AD and those without elevated amyloid. We hypothesize that aerobic exercise will attenuate hippocampal atrophy (1° imaging outcome measure), an area of accelerated atrophy in preclinical AD. Additionally, we will examine the effect of exercise on secondary measures of precuneal and whole-brain atrophy.

Aim 3: Determine the effects of aerobic exercise on cognition in individuals with preclinical AD and those without elevated amyloid. We hypothesize that aerobic exercise will provide cognitive benefits in our primary outcome measure of executive function and in secondary measures of memory and visuospatial function. Additionally, we expect that improvements in memory will correlate with structural preservation in hippocampus.

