This is a randomized controlled trial of 52 weeks of aerobic exercise on sedentary individuals with preclinical AD (n=70) and those with non-elevated cerebral amyloid (n=50) The KU ADC will screen a total of 400 cognitively normal older adults with Florbetapir PET to achieve our enrollment goal. Participants will be randomized in a 2:1 ratio to active aerobic exercise vs. control using randomization sequences generated by the study statistician ([name]). Exercise interventions will be rigorously controlled and supervised in a community-based network of KUMC approved facilities across the Kansas City area. Given our history of 5% drop out over a 6-month exercise trial, we are projecting a 15% annual dropout rate. Participants will have Florbetapir PET and MRI before and after 52 weeks of exercise. Cognitive testing will be completed at baseline, 26-, and 52 weeks. Figure 1 provides an overview of the screening and study events described in more detail below.

Fig. 1 Study Flow and Events

Timeline and Overview of Study Events

Timeline: We anticipate initiating screening of participants within 2 months of funding and beginning enrollment and the intervention within 4 months. Enrollment will be ongoing with screening of 400 participants occurring over three years (~ 3 participants a week) with enrollment completed in the middle of the 4th year of the grant. The final participants will complete the 52-week intervention in the middle of the 5th year, allowing time to complete data analyses and prepare manuscripts.

Screening: The KU ADC will screen a total of 400 participants 65 years of age and older to establish a sufficient cohort (n~120 given an estimated 30% will have evidence of cerebral amyloid) to enroll 70 preclinical AD and 50 amyloid nonelevated participants into the intervention. Screening will include a standard clinical and cognitive evaluation (KU ADC Registry or similar cognitive impairment screening) and Florbetapir PET.

Baseline Evaluation: The baseline evaluation will consist of the following outcome assessments (methodological details provided below) : brain MRI, cognitive testing, physical function assessment (aerobic fitness testing for VO₂ peak, DEXA scan for body composition, and physical function), , physical activity, and phlebotomy.

[figure not shown]
26-Week Evaluation: At 26 weeks (+/- 1 week),, participants will return for an in-person evaluation to repeat cognitive testing and assessments of physical activity.

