Inclusion criteria include

- CDR 0 (nondemented)
- Age 65 or older
- Florbetapir PET evidence of cerebral amyloidosis
- Non-elevated Florbetapir PET scan algorithm computerized measuring a mean quantitative standard uptake value ratio equal to or greater than 1.0 for 6 regions of interest.
- Sedentary or underactive by the Telephone Assessment of Physical Activity
- Stable doses of medications for 30 days.
- Clinician judgment regarding subject's health status and likelihood to successfully complete the 1-year exercise intervention

Exclusion criteria include

- Clinically significant major psychiatric disorder (e.g., Major Depressive Disorder) according to DSM-IV criteria or significant psychiatric symptoms that could impair the completion of the study
- Clinically-significant systemic illness that may affect safety or completion of the study
- History of clinically-evident stroke
- Clinically-significant infection within the last 30 days
- Active cardiac condition (e.g. angina, myocardial infarction, atrial fibrillation) or pulmonary condition in the past 2 years that, in the investigator's opinion, could pose a safety risk to the participant—unless cleared for exercise by the participant's primary care physician or cardiologist.
- Uncontrolled hypertension within the last 6 months
- History of cancer in the last 5 years (except non-metastatic basal or squamous cell carcinoma)
- History of drug or alcohol abuse as defined by DSM-IV criteria within the last 2 years
- Insulin-dependent diabetes mellitus
- Significant pain or musculoskeletal disorder prohibiting participation in an exercise program
- Unwillingness to undergo or contraindication to brain MRI scan.
- History within the last 5 years of primary or recurrent malignant disease with the exception of resected localized cutaneous squamous cell carcinoma, basal cell carcinoma, cervical carcinoma, or prostate cancer.

Non-elevated Amyloid Group: We will recruit individuals with non-elevated amyloid PET scans who have a mean SUVR (in 6 regions of interest) of 1.0 and greater to be enrolled into the trial as part of the non-elevated amyloid group. Based on our first 84 non-elevated participants screened for the study, this represents about 1/3rd of those with non-elevated amyloid PET scans. Participants will be recruited by letter or phone calls to those who have been previously screened and meet the criteria or during in-person screening

APEX Protocol 22 April 2016

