visits until a total of 50 nonelevated participants are enrolled.

SUVR (Standard Uptake Value Ratio) represents a ratio of the retention of radiotracer in the brain compared to the patient's control region of the cerebellum. A higher is believed to reflect higher levels of amyloid in the brain although in this group of individuals who do not evidence of amyloid deposition given their non-elevated status, the relevance of the SUVR value remains uncertain. Nevertheless, this group is of scientific interest given some early data suggesting the group may be enriched with individuals who accumulate amyloid over time.

Rationale for not disclosing SUVR values: Participants will be informed that they are in a group representing 1/3rd of those with non-elevated scans that have been selected as eligible to participate based on computer algorithm. Our current practice is not to communicate information on patient's SUVR values and we believe this continues to be important until more data is available to suggest that SUVR values are shown to be clinically relevant. There is currently no consensus or evidence that within non-elevated participants SUVR values have clinical relevance. It remains unclear that an SUVR value, especially in the non-elevated range, provides any predictive information on risk. Additionally, it remains unclear whether the sensitivity and precision of the measure influences how these values can be interpreted. Not disclosing SUVR values to participants is the current practice for the national Alzheimer's Disease Neuroimaging Initiative. We have a scientific interest in the group of individuals in the top third of SUVR measures as there is early evidence that those with higher amyloid burdens may accumulate amyloid at a more rapid rate than others. Whether individuals who accumulate amyloid are at higher risk of cognitive change is not yet known although given that our primary aim is to assess the impact of aerobic exercise on amyloid accumulation.

Given the burden and expense of amyloid scanning, MRI scanning, and a one-year exercise program, it is not feasible to enroll a sample of all non-elevated participants.

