Rationale: Amyloid imaging has promise as a potential biomarker for identifying the preclinical stages of AD and is being used as an outcome measure to assess biological effects of therapies in clinical trials. This study uses amyloid imaging to 1) identify individuals with early AD pathophysiologic changes (preclinical AD) who are likely at higher risk of developing AD, and 2) to assess potential disease-modifying effects of exercise on early AD pathophysiology. Amyloid imaging techniques have demonstrated sensitivity to change in response to therapeutic agents (Bapineuzumab, see power analyses below).¹¹⁹ Additionally, amyloid burden increases longitudinally in nondemented older adults, with the greatest increase observed in individuals who are amyloid elevated at baseline (i.e., similar to our preclinical AD cohort).¹²⁰ As animal studies¹⁵⁻¹⁷ and indirect human data^{97, 98} suggests exercise modifies the AD pathophysiologic cascade, we hypothesize that aerobic exercise will be associated with reduced cortical amyloid burden over 52 weeks compared to controls.

Preliminary Experience: We have performed 21 Florbetapir PET scans through several clinical trials (ADNI, IGIV, Bapineuzumab). Our nondemented sample (n=10, mean age 82) had 4 of 10 individuals with an amyloid burden similar to that seen in our AD sample (n=11, mean age 76), 10 of 11 whom demonstrated elevated amyloid burden (Figure 2).

Data Acquisition: Florbetapir PET imaging will be obtained at screening and after 52 weeks of exercise (+/- 1 week). Subjects will have a catheter placed for IV administration of Florbetapir F 18 Injection. Vital signs will be taken in a supine position immediately prior to administration of Florbetapir (within 5 minutes). Subjects will receive a single IV bolus of Florbetapir (370 MBq) followed by brain PET imaging of 10 minutes duration, approximately 50 minutes post-dose injection. Adverse events will be continuously monitored during the imaging session and a participant will have follow-up phone call within 2 business days after the imaging session to confirm patient well-being and to collect information about any new adverse events.

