We have identified primary endpoints for intent-to-treat analyses between treatment groups within each study aim: change in amyloid burden (Aim 1); hippocampal atrophy (Aim 2); and change in executive function (Aim 3). Other endpoints and analyses will be described in resulting publications as secondary. For all analyses the traditional type I error rate of $\alpha=0.05$ will be used. We will use two-sided tests to further protect against spurious results. Our primary intent-to-treat analyses will be based on the two-sample t-test. **Table 2** presents the power for each aim of our study corresponding to our primary measures. Anticipated effect sizes are presented using Cohen’s d (expected average group difference divided by the assumed, common standard deviation). We assumed 15% of our 100 enrolled subjects will be lost to attrition, so power calculations assumed 56 subjects in our exercise intervention arm and 28 subjects in our control group.

Table 2. Anticipated study power

Study aim	Primary measure*	Effect size (Cohen’s d)	Power
Aim 1	Amyloid burden	0.79	92.9%
Aim 2	Hippocampal volume	0.66	81.4%
Aim 3	Executive function	2.32	>95%

*Primary measures are change from baseline to 52-week follow-up.

Aim 1: A 78 week study assessing Bapineuzumab¹¹⁹ in AD demonstrated a mean change in cortical PIB retention (average across six cortical regions) of -0.09 (0.16 SD) for those treated with Bapineuzumab (n=20) and 0.20 (0.09) for those on placebo (n=7). Given the differences in our proposed study (preclinical AD sample, lower expected amyloid burden, shorter duration) we determined power allowing exercise to have a lower effect size. An effect size only 40% as large will produce a Cohen’s d of 0.79. Thus, Aim 1 will have 93% power to detect this conservative anticipated effect of exercise on amyloid burden (and 81.9% power to detect 30% of the Bapineuzumab effect size).

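### The protocol states only an overall 2:1 randomisation and does not say that it is stratified by amyloid group, and the pooled primary tests carry no amyloid-group term

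*Combined protocol and SAP*

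**What the plan says.** **Allocation.** Study Procedures says: "Participants will be randomized in a 2:1 ratio to active aerobic exercise vs. control using randomization sequences generated by the study statistician". Specific Aims and Statistical Analyses for Aim 1 also give a 2:1 ratio and nothing more. No section names a stratification factor, block size, minimisation or a separate sequence for each amyloid group. No section says that the randomisation is unstratified either.

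**Enrolment.** Specific Aims sets the sample of 120 as "70 with preclinical AD and 50 with nonelevated amyloid". The section Non-elevated Amyloid Group continues recruitment through screening "visits until a total of 50 nonelevated participants are enrolled". Group size is therefore fixed; the number of controls inside each group is not. Under Clinical and Cognitive Evaluation, eligibility rests on the screening PET scan, so amyloid status is known before allocation.

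**Expected course.** The Aim 1 Rationale says that amyloid rises over time in nondemented older adults, "with the greatest increase observed in individuals who are amyloid elevated at baseline".

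**Analysis.** The primary analyses for Aims 1, 2 and 3 are two-sample t-tests on the 52-week change, comparing the two arms with both amyloid groups pooled. None has an amyloid-group term. The aims are worded for both groups, but no test within a group and no treatment-by-group interaction is specified.

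**The concern.** Amyloid group is the structural factor of this design: it sets the quotas, appears in every aim and, on the plan's own account, predicts the Aim 1 endpoint. The usual practice is to hold the allocation ratio within such a factor, and the text as written does not do so.

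Two things are at stake. If the arms differ by chance in their share of elevated participants, part of the observed arm difference reflects amyloid group, and the unadjusted t-test leaves it there. And the non-elevated group, where 2:1 gives only about 17 controls out of 50, could end with noticeably fewer. A covariate can repair the first problem, but it cannot supply missing controls.

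**Working it through.** **1. The plan's own power figures.** Sample Size Justification uses a two-sided 5% test with 56 versus 28 completers. By the normal approximation, power = Φ(d/√(1/56 + 1/28) − 1.96), and √(1/56 + 1/28) = 0.2315.
- Aim 1, d = 0.79: Φ(3.413 − 1.96) = 92.7% (noncentral t: 92.1%); stated 92.9%.
- Aim 2, d = 0.66: Φ(2.851 − 1.96) = 81.4% (noncentral t: 80.5%); stated 81.4%.

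Both reproduce. The section starts from a smaller sample ("We assumed 15% of our 100 enrolled subjects will be lost to attrition") and does not split by amyloid group, so it says nothing about controls per group. Stratification would not change these figures.

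**2. Controls per group.** Inputs: 120 enrolled, 50 of them non-elevated; 2:1 gives 80 exercise and 40 control.
- *Stratified 2:1:* 50/3 = 16.7 non-elevated controls (16 to 17) and 70/3 = 23.3 elevated controls (23 to 24).
- *One 80:40 list, groups in random order:* the number k of non-elevated controls is hypergeometric, with mean 40 × 50/120 = 16.7 and SD √(40 × 50/120 × 70/120 × 80/119) = 2.56. The 95% range is 12 to 22, leaving 18 to 28 elevated controls.
- *Simple randomisation:* binomial(50, 1/3), SD 3.33, 95% range 10 to 23.

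**3. Arm imbalance, one 80:40 list.** The arm difference in share non-elevated (equal in size to that in share elevated) is k/40 − (50 − k)/80 = (3k − 50)/80. Its SD is 2.557 × 3/80 = 0.096.

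| Difference between arms | Values of k | Probability |
|---|---|---|
| at least 10 points | ≤14 or ≥20 | 0.198 + 0.133 = 33% |
| more than 10 points | ≤13 or ≥20 | 0.106 + 0.133 = 24% |
| more than 15 points | ≤12 or ≥21 | 0.050 + 0.066 = 12% |

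The value k = 14 gives exactly 10 points, so the wording of the threshold matters.

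**4. Shift in the treatment effect.** Shift = imbalance × g, where g is the difference between amyloid groups in mean change, in within-group SD. The documents give no g, so a range is assumed. The 95% range of the shift is ±1.96 × 0.0959 × g. For comparison, the treatment standard error with 15% dropout (120 × 0.85 = 102; 68 versus 34) is √(1/68 + 1/34) = 0.21 SD.

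Leaving group out of the model raises the SD to √(1 + (50 × 70/120²)g²), which lowers the effective d. With group in the model, power at 68 versus 34 is 96% (Aim 1) and 88% (Aim 2).

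| Assumed g | 95% chance shift (SD) | Aim 1 power without group term | Aim 2 power without group term |
|---|---|---|---|
| 0.25 | ±0.05 | 96% | 87% |
| 0.5 | ±0.09 | 95% | 86% |
| 1.0 | ±0.19 | 92% | 80% |

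**5. Precision within the non-elevated group.** The standard error is proportional to √(1/c + 1/(50 − c)) for c controls: 0.299 at 17, 0.331 at 12 (11% wider), 0.354 at 10 (18% wider) and 0.285 at 22 (5% narrower).

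**The case against.** **Silence is not a statement.** A reader might infer that the randomisation is unstratified. The documents do not say so: the statistician's sequences are mentioned in the plural and are not shown, and the study-flow figure is missing from the text available. The supportable statement is that stratification is not stated. This stands.

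**The random-order scenario is an upper one for a blocked list.** The wording "Based on our first 84 non-elevated participants screened for the study" suggests that this group was defined after screening had begun. A reader might conclude that the current amendment added it, but no change log says which version did. If elevated participants were enrolled earlier on one blocked list, the figures shrink. With 30 of them already allocated 2:1 (an assumption), differences above 10 points fall to 18% and above 15 points to 7%. With 45 already allocated, these are 12% and 4%, and non-elevated controls range from 13 to 20. This stands, although blocking is not stated either and simple randomisation gives a wider spread.

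**Slower change in the non-elevated group is only partly supported.** It is direct for amyloid alone. Even there, this group is selected from the top third of non-elevated SUVR values because it may contain more accumulators. For atrophy, the Aim 2 Preliminary Experience text compares preclinical AD with the site's earlier nondemented sample, not with this group. For executive function no difference is stated. This narrows the prognostic argument but does not remove it for the Aim 1 endpoint.

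**The consequence is small, and no within-group test is planned.** Chance imbalance neither biases the randomised comparison on average nor invalidates the pooled test. That is right and limits the weight of the point. Still, every aim is worded for both groups, so readers will look for group-specific estimates.

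**Conclusion.** The point holds as a modest design improvement. The plan gives only an overall 2:1 ratio, does not state stratification by a factor that defines its quotas and aims, and does not adjust for that factor in the primary tests.

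The stronger reading, that the primary comparison is biased or invalid, is not supported. At an assumed between-group difference of 0.5 SD, the chance shift stays within about ±0.09 SD in 95% of trials, less than half of one treatment standard error, and omitting the group term costs about 1 to 2 points of power. Only near 1.0 SD does the cost become noticeable, at 8 points for Aim 2. Within the non-elevated group, 12 controls instead of 17 widens the standard error by about 11%.

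These figures rest on 120 enrolled, one list with exactly 40 controls, random arrival order, 15% dropout and the assumed range of 0.25 to 1.0 SD. What justifies action is that the remedy is nearly free and, for controls per group, works only before participants are allocated.

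**What to change.** In Study Procedures, replace the allocation sentence with wording such as: *Randomisation is 2:1 in permuted blocks of varied size, from separate lists for amyloid-elevated and non-elevated participants.* Apply it to participants not yet randomised and keep existing allocations. If separate lists are already in use, say so; that settles the allocation part.

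In the statistical analysis sections for Aims 1, 2 and 3, add amyloid group as a covariate, so that the t-test on change becomes a linear model with arm and amyloid group. This also covers participants allocated before the change.

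The cost is one extra list and one model term. With two strata of 70 and 50, over-stratification is not a concern.
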